3.6.2 Deaths and Treatment Discontinuations due to Adverse Events

A listing of any deaths will be provided which will include the MedDRA system organ class and preferred term. AEs resulting in permanent discontinuation from study drug will be summarized by study part and treatment. The summary will include results summarized overall and by MedDRA System Organ Class and Preferred Term.

3.6.3 Clinical Laboratory Evaluation

Hematology, serum chemistry, and urinalysis laboratory evaluations will be performed during the study. The hematology and serum chemistry (including calcitonin, lipase, and amylase) parameters as well as their changes from baseline will be summarized with descriptive statistics (number of subjects, mean, and standard deviation, median, minimum and maximum) by study part and treatment group. Other laboratory parameters collected will be summarized in a similar manner. The hematology and serum chemistry results will also be classified as low, normal, or high. The urinalysis results will be classified as normal or abnormal. The shift from baseline hematology, serum chemistry, and urinalysis results will be summarized by study part and treatment at each evaluation time.

3.6.4 Other Safety Evaluations

3.6.4.1 Vital Signs

Vital signs including pulse rate (beats/min), systolic and diastolic blood pressure (mmHg), temperature (oC), and respiratory rate (breaths/min), as well as the change from baseline for each of those parameters, will be descriptively summarized study part and treatment.

3.6.4.2 Electrocardiogram

Electrocardiogram parameters will be assessed with a single ECG at each evaluation (Screening, Day 1, and Day 26) using a digitally recorded standard 12-lead electrocardiograph. The ECG parameters: Heart rate, RR, PR, QRS and QT intervals as well as derived parameter QT corrected interval QTcF (Fridericia's formula $\frac{QT}{\sqrt[3]{RR}}$) will be summarized. The results at Day 26 as well as the change from baseline (Day 1) will be descriptively summarized by study part and treatment. For the qualitative variable ECG interpretation, the ECG Interpretation results will be summarized with frequencies and percentages at each evaluation.

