Subjects will leave the clinical unit on Day 8 with sufficient investigational product to dose themselves every day until returning to the clinical unit on Day 33. Site staff will make remote contact with subjects on Days 14 or 15 and 21 or 22 to remind them to make an uptitration step if required per randomisation and to collect information regarding adverse events and concomitant medications. Contact may be made the day prior to the titration step being made to serve as a reminder, ideally by telephone, but any means of contact where confirmation of information receipt is acceptable and should be made prior to the time that the dose is scheduled on Days 15 and 22.

On Day 33 subjects will be re-admitted to the clinical unit for a further 3 night inpatient stay and as before will receive standardised solid meals during this period. On the evening of Day 34, subjects will fast and be given $^2\text{H}_2\text{O}$ to drink at 2 timepoints during the overnight period. On Day 35, following an MRS scan and blood sampling, subjects will administer their final SC dose of investigational product and then undergo an MMTT as before at T = 0 with serial blood samples collected as before and MRS scans performed at T = 5 and 14 hours.

[figure not shown]
On Day 36, following an overnight fast, a final MRS scan and blood sampling will be performed at T = 24 hours. A follow up visit will be performed 28 days after the last dose of investigational product for safety assessments.

Figure 1 Study Flow Diagram Part A

²H₂O = deuterated water (administration); IP = investigational product; MMTT = mixed-meal tolerance test; MRS = magnetic resonance spectroscopy; SM = standardised meal.

Note that timings may change according to schedule – see schedule of procedures ([Table 6](#), [Table 7](#), and [Table 8](#)) and in an example timetable provided in [Section 10.8](#).

Figure 2 Study Flow Diagram Part B

$^2\text{H}_2\text{O}$ = deuterated water (administration); IP = investigational product MMTT = mixed-meal tolerance test; MRS = magnetic resonance spectroscopy; SM = standardised meal.

Note that timings may change according to schedule of study procedures (Table 6, Table 7, Table 8, Table 9, Table 10, and Table 11) and in an example timetable provided in Section 10.8.

The endpoints to be measured in this study are described in Section 2.

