^a Investigational product administration should occur in the clinic on Day 1 (Visit 2) after the final MRS scan and blood sample collection (Day 1 first dose of MEDI0382 100 µg Daily investigational product administration should then be performed by the subject at home on Day 2 through Day 7 (Day 7 is the last dose of MEDI0382 at a dosage level of 100 µg. The subject will receive the first dose of MEDI0382 200 µg in clinic on Day 8 (Visit 3) at any time in the morning during the clinic visit. The subject will then self-administer investigational product at home daily on Day 9 through Day 14 (Day 14 is the last dose of MEDI0382 at a dose level of 200 µg. The subject will receive the first dose of MEDI0382 300 µg in the clinic on Day 15 (Visit 4) at any time in the morning after blood sampling for PK. The subject will then dose at home daily on Day 16 through to Day 25. MEDI0382 300 µg will be administered in the clinic at on Days 26, 27 and 28; the final dose is on Day 28 (Visit 5).

^r MEDI0382 or placebo will be dispensed on Days 1, 8, and 15.

Table 8 Schedule of Treatment Period Study Procedures (Day 25 through Day 29) (Part A)

Visit Number	Outpatient	Treatment Phase			
		V5			
		Inpatient			
Procedure / Study Day	Day 25	Day 26	Day 27	Day 28 ^a	Day 29
Metformin washout for 5 days ^b	X	X	X	X	X
Admission to the clinical unit		X			
Assessment of AE/SAEs ^c and review of concomitant medications		X	X	X	X
Discharge from the clinical unit					X
Fasting overnight for a minimum of 14 hours required			X	X	
Physical examination (abbreviated), ECG, and urine (or serum) pregnancy test		X			
Weight and urinalysis					X
Vital signs (BP, pulse, body temperature, respiratory rate)		X			X
Collection of blood samples for: ^a					
Serum chemistry, haematology, HbA1c, serum calcitonin, amylase, and lipase					X
Fasting amino acids, FFAs, lipids, BHB, acetoacetate and lactate				X	
MEDI0382 Pharmacokinetics ^d				X	
Immunogenicity (ADA) ^a				X	
Blood samples for non-genetic future research ^e				X	X
Blood samples for 2H labelled glucose ^f			X	X	X
██████████				X	

Table 8 Schedule of Treatment Period Study Procedures (Day 25 through Day 29) (Part A)

Visit Number	Study Period	Outpatient	Treatment Phase			
			V5			
			Inpatient			
Procedure / Study Day	Day 25	Day 26	Day 27	Day 28 ^a	Day 29	
Standardised meals ^b		X	X	X		
Deuterated water (2H ₂ O) administration ^c			X			
MMTT and serial blood sampling for glucose levels ^d				X		
Serial MRS scans ^e				X	X	

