^q Investigational product administration should occur in the clinic on Day 1 (Visit 2) after the final MRS scan and blood sample collection (Day 1 first dose of MEDI0382 50 µg or 0.6 mg liraglutide). Daily investigational product administration should then be performed by the subject at home on Day 2 through Day 7 (Day 7 is the last dose of MEDI0382 at a dosage level of 50 µg or liraglutide 0.6 mg). The subject will receive the first dose of MEDI0382 100 µg or liraglutide 1.2 mg in clinic on Day 8 (Visit 3) at any time in the morning. The subject will then self-administer investigational product at home daily on Day 9 through to Day 14 (Day 14 is the last dose of MEDI0382 at a dose level of 100 µg or liraglutide 1.2 mg). On Day 14 or the morning of Day 15 prior to dosing, the site will make remote contact with the subject and remind them to make the up-titration in the MEDI0382 or placebo arms to 200 µg or liraglutide to 1.8 mg and to continue daily dosing at home. On Day 22 subjects in the MEDI0382 or placebo arms will be asked to uptitrate to 300 µg and to continue this dose until their next visit. Subjects in the liraglutide arm will be advised to continue at a dose at 1.8 mg and to continue this dose until their next visit.

^r MEDI0382 or placebo and liraglutide will be dispensed on Days 1 and 8.

^s #Up-titration in blinded arms only

Table 10 Schedule of Treatment Period Study Procedures (Day 32 through Day 36) (Part B)

Visit Number	Outpatient	Treatment Phase				
		V6				
		Inpatient				
Procedure / Study Day	Day 32	Day 33	Day 34	Day 35 ^a	Day 36	
Metformin washout for 5 days ^b	X	X	X	X	X	
Admission to the clinical unit		X				
Assessment of AE/SAEs ^c and review of concomitant medications		X	X	X	X	
Discharge from the clinical unit						X
Fasting overnight for a minimum of 14 hours required			X	X		
Physical examination (abbreviated), ECG, and urine (or serum) pregnancy test		X				
Weight and urinalysis						X
Vital signs (BP, pulse, body temperature, respiratory rate)		X				X
Collection of blood samples for: ^a						
Serum chemistry, haematology, HbA1c, serum calcitonin, amylase, and lipase						X
Fasting amino acids, FFAs, lipids, BHB, acetoacetate and lactate				X		
MEDI0382 Pharmacokinetics ^d				X		
Immunogenicity (ADA) ^e				X		
Blood samples for non-genetic future research ^f				X	X	
Blood samples for ² H labelled glucose ^g			X	X	X	
████████████████ ^h					X	

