1 INTRODUCTION

This document describes the statistical analysis methodology for protocol D5670C00022 (Amendment 6, 15Jul2020), a Phase 2 study to evaluate the effect of MEDI0382 on hepatic glycogen levels post prandially versus placebo in Part A and to compare the effect of MEDI0382 on hepatic glycogen levels versus placebo and liraglutide in Part B in overweight or obese subjects with T2DM. This document details the statistical summaries relating to each study objective and describes the general conventions and definitions that will be used. In addition, a set of table templates and specifications will be included in a statistical programming plan (SPP) to complement this document.

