3.8 Pharmacokinetics

The analysis of the pharmacokinetic data is described below. However, the results of these analyses will be provided in the pharmacokinetic report that is prepared by the

pharmacokineticist; therefore no tables, figures or listings of pharmacokinetic data will be specified in the SPP.

Plasma C_{trough} concentrations of MEDI0382 at steady state (Part A Day 15 and Day 28; Part B Day 35) will be summarized with descriptive statistics.

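### SAP 3.6.4.2 summarises post-baseline ECGs only at Day 26, a visit that exists only in Part A; the Part B on-treatment ECG is scheduled for Day 33

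*SAP*

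**What the plan says.** SAP 3.6.4.2 describes the ECG assessment as a "single ECG at each evaluation (Screening, Day 1, and Day 26"), with no distinction between parts. It names the interval parameters and QTcF, then sets the summary rule: "The results at Day 26 as well as the change from baseline (Day 1) will be descriptively summarized by study part and treatment". The investigator's ECG interpretation is tabulated at each evaluation, which refers back to the same three days.

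The protocol schedules the treatment-period ECG by part. Tables 8 (Part A) and 10 (Part B) carry the same row, "Physical examination (abbreviated), ECG, and urine (or serum) pregnancy test". It is marked on the admission day in each: Day 26 in Table 8 and Day 33 in Table 10. Protocol 3.1.1 says that Part B subjects leave the Day 8 visit with enough product to "dose themselves every day until returning to the clinical unit on Day 33".

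The SAP states that it follows the protocol version that contains this schedule ("Amendment 6, 15Jul2020"). It separates days by part elsewhere, for example for PK in SAP 3.8: "Part A Day 15 and Day 28; Part B Day 35".

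**The concern.** The rule puts Part B in scope by asking for results by study part, but the day it names does not occur in Part B. A programmer who follows the text would find no scheduled Part B record at Day 26, and the Part B post-baseline and change-from-baseline cells would be empty.

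ECGs are among the safety measures listed as secondary endpoints (protocol Table 3, SAP 3.4.2.1). QT prolongation is a named potential risk in protocol 1.6 and one of the examples in protocol 4.4 of a reason to suspend or stop the study. Part B holds about half of the planned MEDI0382 subjects and is the only part with a liraglutide arm.

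A secondary gap is that the follow-up ECG, scheduled in both parts by Table 11, is absent from the SAP list. The protocol synopsis has ECG findings summarised at every time point. Protocol 4.8.4.2 is weaker and says only that ECG parameters are summarised descriptively.

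**Working it through.** The plan gives no figure to reproduce. The check compares the SAP's list of days with the protocol schedules.

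**Scheduled ECGs against the SAP list**

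| ECG | Source | Part A | Part B | In SAP 3.6.4.2? |
|---|---|---|---|---|
| Screening | Table 6 | yes | yes | yes |
| Day 1 (baseline) | Tables 7 and 9 | yes | yes | yes |
| On treatment | Tables 8 and 10 | Day 26 | Day 33 | Day 26 only |
| Follow-up, 28 days after last dose | Table 11 | yes | yes | no |

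Each part schedules 4 ECGs per subject.

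- Part A: 3 of 4 are listed; on-treatment 1 of 1; post-baseline 1 of 2.
- Part B: 2 of 4 are listed; on-treatment 0 of 1; post-baseline 0 of 2.

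**Is there any Part B contact on Day 26?** Table 9 ends at Day 22 and Table 10 starts at Day 32. Between the Day 8 visit and Day 33 the only contacts are remote, on Days 14/15 and 21/22. No ECG is scheduled in that interval.

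**Does other SAP text repair the rule?**

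- The SAP gives no visit windows that would map Day 33 to Day 26.
- The laboratory and vital-sign sections (3.6.3, 3.6.4.1) name no days, so they work for both parts.
- The missing-data section for the primary endpoint (3.4.1.2) and the PK section (3.8) name days by part. The ECG section names a Part A day only.

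**Subjects affected, from planned numbers**

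- Part A MEDI0382: up to 20 × 1/2 = 10.
- Part B MEDI0382: about 30 × 1/3 = 10.
- Share of MEDI0382 subjects without an on-treatment ECG summary: 10/(10 + 10) = 50%.
- All Part B subjects, three arms: about 30.

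**Is Day 33 comparable with Day 26 for MEDI0382?** The Part A top dose step starts "in the clinic on Day 15 (Visit 4) at any time in the morning after blood sampling for PK". For Part B the protocol says "On Day 22 subjects in the MEDI0382 or placebo arms will be asked to uptitrate to" the top step. Counting inclusively:

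- Part A: 26 − 15 + 1 = 12th day of the top step.
- Part B: 33 − 22 + 1 = 12th day of the top step.

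Liraglutide reaches its top step on Day 15, so for that arm Day 33 is day 33 − 15 + 1 = 19.

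**What the follow-up ECG measures.** Protocol 3.2.1 gives a MEDI0382 half-life of about 8 to 13 hours. At the nominal 28 days, 28 × 24 = 672 h; 672/13 ≈ 52 and 672/8 = 84 half-lives. With the ±3-day window the range is 25 × 24 = 600 h to 31 × 24 = 744 h; 600/13 ≈ 46 and 744/8 = 93. For MEDI0382 this is an off-drug reading. The documents give no half-life for liraglutide, so the calculation does not extend to that arm.

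**The case against.** The strongest reply is that an empty Part B table is a strained reading. SAP 3.6.4.2 first says without any day limit that the parameters will be summarised. It asks for results by part, which shows that a Part B summary is intended. SAP 3.1 says that all available data enter the analyses, and the synopsis covers every time point. Table templates sit in a separate statistical programming plan, which may already show Day 33. On this view the error is a wrong visit label: Part B has one scheduled on-treatment ECG, so there is no choice of day to make and no room for bias.

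Much of this stands. The intention is clear, and the loss of output depends on following the text literally. But statements of intent do not replace a day that the SAP names explicitly. The programming plan is not among the documents and is described as complementing the SAP. Using Day 33 without amending the SAP would be an undocumented departure from it.

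Some narrower points also stand:

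- That the section was missed when the SAP was brought into line with Part B is an inference. It is supported by the cited amendment and the part-specific days elsewhere.
- Day 33 is the only *scheduled* on-treatment ECG in Part B; protocol 4.3.2.3 lets the investigator add others.
- The 12th-day comparison holds for MEDI0382 but not for liraglutide. It is supporting detail, because Day 33 is in any case the only scheduled candidate.
- The follow-up ECG carries little weight as drug-effect information, and the case for summarising it rests on the synopsis.

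**Conclusion.** The concern holds. As written, SAP 3.6.4.2 gives no scheduled on-treatment ECG summary for Part B: 0 of 1 on-treatment ECGs, against 1 of 1 in Part A. This affects about 30 planned subjects, including about 10 of about 20 on MEDI0382. The counts assume planned enrolment, the stated allocation ratios, and a literal reading of the SAP without help from the programming plan.

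The consequence is confined to descriptive safety output. Part B ECG data are still collected and available for listing, pulse rate is still summarised under SAP 3.6.4.1, and no test or efficacy result depends on the ECG table. The omitted follow-up ECG removes no on-treatment information. The correction should be made, but it does not threaten the trial's conclusions.

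**What to change.** Replace the visit list and summary sentence in SAP 3.6.4.2 with wording such as:

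> ECG evaluations are Screening, Day 1, Day 26 and follow-up in Part A, and Screening, Day 1, Day 33 and follow-up in Part B. Values and changes from Day 1 will be summarised at Day 26 (Part A), Day 33 (Part B) and follow-up, for each study part and treatment group.

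The sentence on ECG interpretation then needs no change, because it takes its days from the corrected list. Check that the statistical programming plan uses the same days.

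The cost is one SAP sentence, a part-specific visit label in an existing table and a follow-up column. No new data are needed and no study procedure changes.

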3.7 Immunogenicity

All subjects in the safety analysis set with reported anti-drug antibody (ADA) results (ADA positive or ADA negative, titer, cross-reactivity to GLP1 (positive or negative), cross-reactivity to glucagon (positive or negative) will be shown in the data listing.

ADA status (positive vs. negative) will be summarized by treatment group according to the following categories:

ADA prevalence: subjects who are ADA positive at any visit (including baseline)

Subjects who are ADA positive at baseline only

Subjects who are ADA positive at baseline and positive post baseline

Subjects who are ADA positive post-baseline only (treatment-induced ADA)

Subjects who are persistently positive; persistently positive is defined as at least 2 post-baseline ADA positive measurements (with ≥ 16 weeks apart) or an ADA positive result at the last available assessment

Proportion of subjects who are transiently positive; transiently positive is defined as at least one post-baseline ADA positive measurement and not fulfilling the conditions for persistently positive.

Proportion of subjects who are treatment-boosted ADA; treatment-boosted ADA is defined as baseline ADA titer that was boosted to a 4-fold or higher level following drug administration

ADA incidence (treatment-emergent ADA), defined as the sum of treatment-induced ADA (post-baseline positive only) and treatment-boosted ADA

Similar summary will be performed for ADA cross-reactivity to GLP-1 and/or glucagon (as data allows and if applicable).

The association of ADA status with PK, PD endpoints, efficacy, and safety may be evaluated if data allows and if applicable.

3.8 Pharmacokinetics

The analysis of the pharmacokinetic data is described below. However, the results of these analyses will be provided in the pharmacokinetic report that is prepared by the

pharmacokineticist; therefore no tables, figures or listings of pharmacokinetic data will be specified in the SPP.

Plasma C_{trough} concentrations of MEDI0382 at steady state (Part A Day 15 and Day 28; Part B Day 35) will be summarized with descriptive statistics.

3.9 Protocol Deviations

A summary of important protocol deviations (IPD) will be prepared by deviation category as well as overall. A listing of the important protocol deviations will be also provided.

4 INTERIM ANALYSIS

An interim analysis (ie, Part A analysis) was performed after Part A subjects have completed the study.

